[Part 2 of 2 of the document. The other parts are not shown.]

Appropriate personnel in Biogen Safety and Benefit Risk (SABR) will unblind SUSARs for the purpose of regulatory reporting. Biogen or designee will submit SUSARs (in blinded or unblinded fashion) to regulatory agencies according to local law. Biogen or designee will submit SUSARs to Investigators in a blinded fashion.

15.4. Procedures for Handling Special Situations

15.4.1. Pregnancy

Subjects should not become pregnant or impregnate their partners during the study and for 24 weeks after their last dose of study treatment. If a female subject becomes pregnant, study treatment must be discontinued *immediately*.

The Investigator must report a pregnancy occurring in a female subject by faxing the appropriate form to [REDACTED] within 24 hours of the study site staff becoming aware of the pregnancy at the SAE reporting fax number provided in the study reference manual. The Investigator or study site staff must report the outcome of the pregnancy to [REDACTED]

Congenital abnormalities and birth defects in the offspring of male or female subjects should be reported as an SAE if conception occurred during the study treatment period.

15.4.2. Overdose

An overdose is any dose of study treatment given to a subject or taken by a subject that exceeds the dose described in the protocol. Overdoses are not considered AEs and should not be recorded as an AE on the CRF; however, all overdoses must be recorded on an Overdose form and faxed to [REDACTED] within 24 hours of the site becoming aware of the overdose. An overdose must be reported to [REDACTED] even if the overdose does not result in an AE. If an overdose results in an AE, the AE must be recorded. If an overdose results in an SAE, both the SAE and Overdose forms must be completed and faxed to [REDACTED]

CONFIDENTIAL

The information contained herein may not be used, disclosed, or published without the written consent of Biogen MA Inc.

(b) (4). All study treatment-related dosing information must be recorded on the dosing CRF.

15.4.3. Medical Emergency

In a medical emergency requiring immediate attention, study site staff will apply appropriate medical intervention, according to current standards of care. The Investigator (or designee) should contact the (b) (4) 24-hour emergency medical support number. Refer to the Study Reference Guide's Official Contact List for complete contact information.

15.4.3.1. Unblinding for Medical Emergency

In this study, emergency decoding will be made available to the Investigator and designated personnel at Biogen through IRT.

In a medical emergency when knowledge of the subject's treatment assignment may possibly influence the subject's clinical care, the Investigator may access the subject's treatment assignment by IRT. However, prior to unblinding, the Investigator can contact the (b) (4) 24-hour emergency medical support number at (b) (4).

The Investigator must document the reasons for unblinding in the subject's source documents. The Investigator is strongly advised not to divulge the subject's treatment assignment to any individual not directly involved in managing the medical emergency, nor to personnel involved with the analysis and conduct of the study.

15.5. Contraception Requirements

For the purposes of this study, women of childbearing potential are defined as all women physiologically capable of becoming pregnant, UNLESS they meet one of the following conditions:

- Postmenopausal
 - 12 months of natural (spontaneous) amenorrhea without an alternative medical cause or 6 weeks after surgical bilateral oophorectomy with or without hysterectomy.
- Post hysterectomy.
- Female surgical sterilization (e.g., bilateral tubal ligation).

For the purposes of this study, highly effective contraception is defined as use of 1 of the following:

- For females of childbearing potential:
 - Established use of oral, injected, or implanted hormonal methods of contraception.
 - Placement of an intrauterine device or intrauterine system
 - Barrier methods of contraception with use of a spermicide: condom or occlusive cap (diaphragm or cervical/vault caps) with spermicidal foam/gel/film/cream

CONFIDENTIAL

The information contained herein may not be used, disclosed, or published without the written consent of Biogen MA Inc.

suppository. The use of barrier contraceptives should always be supplemented with the use of a spermicide.

- Male sexual partners underwent surgical sterilization with the appropriate postvasectomy documentation of the absence of sperm in the ejaculate.
- For males:
 - Vasectomy with negative semen analysis at FU.
 - Use of condoms with spermicide.
 - Female sexual partners who underwent surgical sterilization (e.g., bilateral tubal ligation), are postmenopausal, are post-hysterectomy, or are using highly effective contraception as listed above for female subjects.

For males and females of childbearing potential:

True abstinence, when this is consistent with the preferred and usual lifestyle of the subject, can be considered an acceptable method of contraception based on the evaluation of the Investigator who should also take into consideration the duration of the clinical trial. Periodic abstinence (e.g., calendar, ovulation, symptothermal, postovulation methods) and withdrawal are not considered acceptable methods of contraception.

Pregnancy reporting is described in Section 15.4.1.

15.6. Safety Responsibilities

15.6.1. The Investigator

The Investigator's responsibilities include the following:

- Monitor and record all AEs, including SAEs, regardless of the severity or relationship to study treatment.
- Determine the seriousness, relationship, and severity of each event.
- Determine the onset and resolution dates of each event.
- Monitor and record all pregnancies and FU on the outcome of the pregnancy in female subjects.
- Complete an SAE form for each SAE and fax it to Biogen SABR (or designee) within 24 hours of the study site staff becoming aware of the event.
- Pursue SAE FU information actively and persistently. FU information must be reported to Biogen SABR (or designee) within 24 hours of the study site staff becoming aware of new information.
- Ensure all AE and SAE reports are supported by documentation in the subjects' medical records.
- Pursue AE FU information, if possible, until the event has resolved or become stable.

CONFIDENTIAL

The information contained herein may not be used, disclosed, or published without the written consent of
Biogen MA Inc.

- Report SAEs to local EC/IRBs, as required by local law.

15.6.2. Biogen

Biogen's responsibilities include the following:

- Before study site activation and subject enrollment, the Clinical Monitor (██████████) is responsible for reviewing with study site staff the definitions of AE and SAE, as well as the instructions for monitoring, recording, and reporting AEs and SAEs.
- Biogen (or designee) is to notify all appropriate regulatory authorities, central EC/IRBs, and Investigators of SAEs, as required by local law, within required time frames.

CONFIDENTIAL

The information contained herein may not be used, disclosed, or published without the written consent of Biogen MA Inc.

16. STATISTICAL METHODS AND DETERMINATION OF SAMPLE SIZE

The objectives of the study and the endpoints to be analyzed are listed in Section 6.

16.1. Demography and Baseline Disease Characteristics

Demographics and baseline data will be summarized by treatment group with summary statistics (mean, standard deviation [SD], median, and range) or with frequency distributions.

16.2. Efficacy and Pharmacodynamics

16.2.1. Analysis Population

The intent-to-treat (ITT) population, defined as all subjects who were randomized and received at least 1 dose of study treatment (aducanumab or placebo), will be used for the efficacy analyses. For each endpoint, additional conditions may apply to the definition of the population for the analysis. Subjects will be analyzed in the groups to which they were randomized.

16.2.2. Methods of Analysis

16.2.2.1. General Considerations

Summary statistics will be presented. For continuous endpoints, summary statistics will generally include: number of subjects with data, mean, standard deviation, median, and range. For categorical endpoints, this will generally include: number of subjects randomized or dosed, number with data, and the percent of those with data in each category. Statistical testing for efficacy endpoints will be made between each aducanumab regimen and placebo. All statistical tests will be 2-sided.

16.2.2.2. Dose Regimens to be Evaluated

The following dose regimens of aducanumab as compared with placebo will be evaluated:

- Aducanumab high-dose regimen (10 mg/kg in ApoE ϵ 4 [including 6 mg/kg for subjects enrolled under protocol version 1-3 who do not have the opportunity to up-titrate to 10 mg/kg prior to completing Week 78 of the study] and 10 mg/kg in ApoE ϵ 4 non carriers).
- Aducanumab low-dose regimen (3 mg/kg in ApoE ϵ 4 carriers and 6 mg/kg in ApoE ϵ 4 non-carriers).

In the event that the maximum dose (10mg/kg) is terminated after the start of the study (Section 5.3.2) the definition of aducanumab high dose regimen and aducanumab low dose regimen will be modified as shown in Table 12. The dosing modification will be entirely based on interim analysis of outcomes that are independent of, and uninformative about, the treatment-related efficacy effect. Control of Type I error rate is thus maintained without a statistical adjustment for such adaptations[Chow and Chang 2011].

CONFIDENTIAL

The information contained herein may not be used, disclosed, or published without the written consent of Biogen MA Inc.

Table 12: Dose Group Pooling Strategy in the Event of Treatment Group Termination

Treatment Group(s) Terminated	Definitions of Revised Pooled Treatment Groups for Comparison
ApoE ε4 carrier high-dose group (10 mg/kg) [including 6 mg/kg for subjects enrolled under protocol version 1-3 who do not have the opportunity to up-titrate to 10 mg/kg prior to completing Week 78 of the study]	Low: ApoE ε4 carrier 3 mg/kg and non-carrier 6 mg/kg High: ApoE ε4 carrier 3 mg/kg and non-carrier 10 mg/kg
ApoE ε4 non-carrier high-dose group (10 mg/kg)	Low: ApoE ε4 carrier 3 mg/kg and non-carrier 6 mg/kg High: ApoE ε4 carrier 10 mg/kg and non-carrier 6 mg/kg
ApoE ε4 carrier high-dose group (10 mg/kg) AND ApoE ε4 non-carrier high-dose group (10 mg/kg)	ApoE ε4 carrier 3 mg/kg and non-carrier 6 mg/kg

16.2.2.3. Considerations for Multiple Comparison Adjustments

A sequential (closed) testing procedure will be used to control the overall Type I error rate due to multiple comparisons for the primary endpoint. The order of treatment comparisons is as follows: aducanumab high-dose regimen versus placebo and aducanumab low-dose regimen versus placebo. All comparisons after the initial comparison with $p > 0.05$ will not be considered statistically significant.

Secondary endpoints have been rank prioritized, in the order shown in Section 6. In order to control for a Type I error for the secondary endpoints, a sequential closed testing procedure will be used and will include both the order of the secondary endpoints and treatment comparisons. Specifically, for each of the secondary endpoints, a sequential (closed) testing procedure, as for the primary endpoint, will be used to control the overall Type I error rate due to multiple treatment comparisons. If statistical significance is not achieved for 1 or 2 comparisons, all endpoint(s) of a lower rank will not be considered statistically significant for 1 or 2, respectively.

Due to a current lack of scientific consensus in the AD field on which biomarker(s) might be most appropriate, the selection of the biomarkers and methodology for control of Type I error will be pre-specified in the statistical analysis plan (SAP). Otherwise, there will be no multiple comparison adjustments for the tertiary endpoints.

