6.2. Secondary Objectives and Endpoints

A secondary objective is to assess the effect of monthly doses of aducanumab as compared with placebo on clinical progression as measured by the MMSE.

- The endpoint that relates to this objective is change from baseline in MMSE score at Week 78.

Another secondary objective is to assess the effect of monthly doses of aducanumab as compared with placebo on clinical progression as measured by ADAS-Cog 13.

- The endpoint that relates to this objective is change from baseline in ADAS-Cog 13 score at Week 78.

Another secondary objective is to assess the effect of monthly doses of aducanumab as compared with placebo on clinical progression as measured by ADCS-ADL-MCI.

- The endpoint that relates to this objective is change from baseline in ADCS-ADL-MCI score at Week 78.

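### The carry-forward rule for secondary endpoints leaves two tests open at the full 0.05, so it does not deliver the Type I error control promised for the secondary family

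*Protocol*

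**What the plan says.** The references are to the latest Section 16 in the document, the one that mentions subjects enrolled under protocol versions 1–3.

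- **Sidedness (16.2.2.1):** "All statistical tests will be 2-sided".
- **Primary endpoint (16.2.2.3, first paragraph):** a sequential procedure is used "to control the overall Type I error rate due to multiple comparisons for the primary endpoint". The order is "aducanumab high-dose regimen versus placebo and aducanumab low-dose regimen versus placebo", with the stopping rule "All comparisons after the initial comparison with $p > 0.05$ will not be considered statistically significant".
- **Secondary endpoints (16.2.2.3, second paragraph):** "Secondary endpoints have been rank prioritized, in the order shown in Section 6". The stated aim is Type I error control for these endpoints, across both their rank and the dose comparisons. Within an endpoint, "for each of the secondary endpoints, a sequential (closed) testing procedure, as for the primary endpoint, will be used". Between endpoints, "If statistical significance is not achieved for 1 or 2 comparisons, all endpoint(s) of a lower rank will not be considered statistically significant"; the closing words apply this to one or two comparisons respectively.
- **Endpoint order:** Section 6 of the latest version is not shown. In version 3.0, section 6.2 starts with MMSE ("The endpoint that relates to this objective is change from baseline in MMSE score at Week 78"), followed by ADAS-Cog 13 and ADCS-ADL-MCI.

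The corresponding sections of versions 1.0 to 3.0 contain the same carry-forward rule, worded for three comparisons.

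**The concern.** A fixed sequence controls familywise error because at any moment only one hypothesis is open, and the first failure ends testing. Here, failure of the low dose on an endpoint ends testing for the low dose only. The high dose goes on to the next endpoint at the full level. After high dose succeeds on endpoint k, two hypotheses are therefore open at once: low dose on k, and high dose on k+1. Each is tested at 0.05 and neither waits for the other.

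Nor is this a closed test at 0.05. When both of these hypotheses are true, their intersection is rejected whenever either test is significant, which happens more than 5% of the time.

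What is at stake is the set of secondary claims. A reader of the results would take significant secondary findings as protected at 5% across endpoints and doses, because section 16.2.2.3 says so. A high dose that works while the low dose lags is an ordinary outcome of a two-dose trial, and that is where the protection fails.

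**Working it through.** **Inputs.** Two-sided 0.05 per test, high before low, per-comparison carry-forward (16.2.2.1, 16.2.2.3). 450 per group, difference 0.5, SD 1.92, 30% drop-out (16.7). 1:1:1 allocation with one placebo group (version 3.0 synopsis). Assumption: a common correlation r between endpoints of 0 to 0.7, since the protocol gives none.

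**The plan's own figure.** Completers per group: 450 × 0.70 = 315. Standard error: 1.92 × √(2/315) = 0.153. Noncentrality: 0.5/0.153 = 3.27. Power: Φ(3.27 − 1.96) ≈ 0.90, which matches the stated 90%. The same noncentrality is used below wherever a true effect has 90% power.

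**Correlation between the two open tests.** With equal arms and a shared placebo group, the high-dose and low-dose statistics on one endpoint correlate 0.5. Across two endpoints the correlation is 0.5 × r.

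**Configuration B, within the secondary family.** Both doses work on CDR-SB and high dose works on MMSE; low-dose MMSE and high-dose ADAS-Cog 13 are null, as is everything ranked lower. With power near 1 for the true effects, a false secondary claim occurs if either open test is significant:

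FWER = 1 − P(|Z₁| < 1.96 and |Z₂| < 1.96), with corr(Z₁, Z₂) = 0.5r.

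At r = 0 this is 1 − 0.95² = 0.0975.

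| r | exact FWER, power near 1 |
|---|---|
| 0 | 0.0975 |
| 0.3 | 0.0969 |
| 0.5 | 0.0959 |
| 0.7 | 0.0943 |

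Even r = 1 gives 0.0907. Simulating the full eight-test rule, with each low-dose test requiring high-dose success on the same endpoint, gives 0.0969, 0.0965 and 0.0945 at r = 0, 0.5 and 0.7. If each of the three true effects has 90% power instead, the simulated error is about 0.072 at r = 0, falling to 0.056 at r = 0.7. It falls because the chain is more often cut before both null tests open.

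**Configuration A, primary plus secondaries.** High dose works on CDR-SB only. The two open null tests are CDR-SB low and MMSE high, so with power near 1 the same formula applies (0.0943–0.0975). At the planned 90% power the simulation gives 0.082, 0.076 and 0.069 for r = 0, 0.5 and 0.7. Counting secondary endpoints alone, the error in this configuration is 0.050 with power near 1. The breach of the secondary promise therefore rests on configuration B.

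**Where the rule does control.** All gave about 0.05 in simulation:
- CDR-SB high then low, taken alone.
- The global null, if secondaries follow a successful primary.
- Both doses meeting their first null on the same endpoint.

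**After the change.** One fixed sequence through the eight tests gives 0.05, within Monte Carlo noise, in configurations A and B with power near 1.

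**The case against.** The best defence is that the leak is narrow. Low dose is tested on an endpoint only after high dose succeeds there, so a reader who pictures two wholly parallel chains goes too far. The CDR-SB sequence is a valid fixed sequence, and the first test and its sample size are untouched. No single test exceeds 5%; what rises is the chance of at least one false claim in a family. All of this stands, and it limits the finding to the secondary family and to the primary and secondary endpoints taken together.

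It also stands that section 16.2.2.3 makes separate promises for the primary and for the secondaries. The pooled error in configuration A therefore breaks no stated promise by itself. Configuration B does, because both false claims are secondary.

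The values above 9% are near-worst cases: they need power near 1 and exact nulls in particular places. The 90%-power figures are the more moderate guide, and they too exceed 5%.

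One might read the rule so that any miss stops everything. That would control the error, but it leaves the words tying the block to one or two comparisons respectively without a purpose.

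A reader might also infer that the secondaries can be tested even if the primary fails. The document does not say so. It is silent on gating, which is a detail often left to the SAP, and no error rate should be built on that silence.

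**Conclusion.** The point holds for the secondary family. Section 16.2.2.3 states a specific rule and attributes to it a control that it does not have. Within the secondaries, familywise error reaches about 9.4–9.8% in configuration B with power near 1, and about 5.6–7.2% with 90% power for each true effect. Across primary and secondaries, with high dose effective on CDR-SB only, it is about 9.4–9.8% and 6.9–8.2% respectively. These figures assume 1:1:1 allocation, two-sided 0.05 for each test and endpoint correlations of 0 to 0.7. The endpoint order is taken from version 3.0, but another order would only relabel the endpoints and would not remove the branching.

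The rule is not deferred to the SAP: in this section only the biomarker multiplicity is. The confirmatory claim on CDR-SB is unaffected, so this is a should-fix item, not a threat to the primary analysis.

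**What to change.** Replace the last sentence of the second paragraph of 16.2.2.3 with one of these:

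1. **Single fixed sequence:** CDR-SB high, CDR-SB low, MMSE high, MMSE low, ADAS-Cog 13 high, ADAS-Cog 13 low, ADCS-ADL-MCI high, ADCS-ADL-MCI low, stopping at the first non-significant result.
2. **Graphical procedure**, if high-dose secondaries must survive a low-dose miss: after CDR-SB high succeeds, split alpha between a low-dose branch and a high-dose secondary branch (an equal split would be 0.025 + 0.025 = 0.05), with the transfer of unused alpha specified in advance.

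Run either at the overall two-sided 0.05, or at the final-analysis level if the O'Brien-Fleming superiority interim of 16.6.2 is performed. State outright that secondaries are tested only after the high-dose CDR-SB test succeeds. Carry the same text into the SAP.

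**Cost:** wording only, with no change to sample size or to the first test. Under option 1, a low-dose miss on CDR-SB ends all secondary claims, including those for the high dose. Under option 2, some claims face a smaller alpha. The sponsor should choose according to which claims matter more, before any unblinding.

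### The secondary-endpoint testing rule stops only the regimen that failed, so it is not a closed test and its family-wise error can reach about 0.091 to 0.0975 in the worst case

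*Protocol*

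**What the plan says.** Three parts of Section 16.2.2.3 in the latest protocol version (the one with two regimens) matter here.

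- **The promise.** "In order to control for a Type I error for the secondary endpoints, a sequential closed testing procedure will be used", and the procedure "will be used and will include both the order of the secondary endpoints and treatment comparisons". Doses and endpoints are thus meant to sit inside one procedure.
- **Within an endpoint.** The doses follow the primary-endpoint pattern: "a sequential (closed) testing procedure, as for the primary endpoint, will be used to control the overall Type I error rate". That pattern is "The order of treatment comparisons is as follows: aducanumab high-dose regimen versus placebo and aducanumab low-dose regimen versus placebo", with the stopping rule "All comparisons after the initial comparison with $p > 0.05$ will not be considered statistically significant".
- **Across endpoints.** "If statistical significance is not achieved for 1 or 2 comparisons, all endpoint(s) of a lower rank will not be considered statistically significant"; the sentence then ends by saying to which comparisons the block applies: "endpoint(s) of a lower rank will not be considered statistically significant for 1 or 2, respectively".

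Section 16.2.2.1 adds "All statistical tests will be 2-sided". The rank order, from Section 6.2 of the bundled versions and matched by the order of Section 16.2.2.5, is MMSE, ADAS-Cog 13, ADCS-ADL-MCI.

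**The concern.** The closing words of the cross-endpoint sentence carry a failure forward for each regimen separately. If only low dose fails on MMSE, only low dose is barred from ADAS-Cog 13, and high dose goes on at 0.05. Low dose on MMSE was itself tested at 0.05. One rejection, high dose on MMSE, has therefore passed the whole 0.05 to two hypotheses at once.

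A fixed sequence can pass its alpha to one successor only. A closed test would need a 0.05-level test of the intersection of those two nulls. Here that intersection is rejected whenever either p-value is at most 0.05.

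At stake are the secondary claims. Low dose on MMSE, or high dose on ADAS-Cog 13 or ADCS-ADL-MCI, could be reported as significant under Type I control that the written rule does not deliver.

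**Working it through.** **Inputs from the protocol.** Every comparison is two-sided at 0.05. High dose precedes low dose. Failures carry forward per regimen. Groups are equal (450 each, Section 16.7; 1:1:1 in Sections 7.1 and 9.2 of the bundled versions).

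**Not in the protocol.** It gives neither the correlation r between endpoints nor the power on MMSE. Both are assumptions, shown as ranges.

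**The plan's own figures.** Section 16.7: n = 450 × 0.7 = 315 per group, standard error = 1.92 × √(2/315) = 0.153, 0.5/0.153 = 3.27, and power = Φ(3.27 − 1.96) = 0.905. The stated 90% reproduces, but it is for the primary endpoint. The 0.05 level reproduces when all secondary nulls are true: nothing opens until high dose on MMSE is rejected, and simulation gives 0.050.

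**The rule as written.** Let H1, H2, H3 and L1, L2, L3 be the high- and low-dose tests in rank order.

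- Hk is tested if H(k−1) was rejected.
- Lk is tested if Hk and L(k−1) were both rejected.
- Once H1 is rejected, L1 and H2 are therefore both open at 0.05.

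**Worst case.** H1 is a true effect with power near 1, and L1 and H2 are null. The error is P(|Z_L1| > 1.96 or |Z_H2| > 1.96). Each contrast is a difference of two independent arm means with equal variance. The two contrasts share only the placebo arm, so their correlation is r/2. At r = 0 the error is 1 − 0.95² = 0.0975. For other r the bivariate normal gives:

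| r | correlation r/2 | error |
|---|---|---|
| 0 | 0 | 0.0975 |
| 0.3 | 0.15 | 0.0969 |
| 0.5 | 0.25 | 0.0959 |
| 0.7 | 0.35 | 0.0943 |
| 0.8 | 0.40 | 0.0932 |
| 1 | 0.50 | 0.0907 |

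The Bonferroni bound is 0.10. Simulating the whole rule (1,000,000 trials per setting) gives 0.0975, 0.0959 and 0.0936 at r = 0, 0.5 and 0.8. The fork recurs one rank lower, with high dose effective on MMSE and ADAS-Cog 13 and low dose on MMSE only: 0.0972, 0.0959 and 0.0935.

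**Other configurations** (simulated; where three values are given, r = 0.3 / 0.5 / 0.7):

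- Fork case, H1 at 90% power (mean z 3.24): 0.079 / 0.075 / 0.069.
- Fork case, H1 at 80% power: 0.069 / 0.065 / 0.058.
- Fork case at 90% power, with both regimens also having to pass the primary endpoint at 90% power: 0.063 at r = 0.5.
- High dose effective on all three endpoints, low dose null on all: about 0.039 at 90% power each, 0.050 with power near 1.
- Both doses effective on MMSE at 90% power each, all else null: 0.043 / 0.039 / 0.033.

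**After repair.** A single sequence that stops at the first failure has a maximum of 0.050, within simulation noise. Two regimen chains at 0.025 each have a maximum of about 0.049.

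**The case against.** The case for the plan has four parts.

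- **The inflation is conditional.** It needs high dose to work on one endpoint and be null on the next, with low dose null on the first. Elsewhere the error is 0.05 or less, and no passage supports power near 1 on MMSE. This stands, and it rules out an inference that a reader might draw: that the secondary error rate simply is about 0.095. That is the top of the range over configurations.
- **These are not two free-standing branches at 0.05 each.** Low dose also needs high dose to have won on the same endpoint. This stands too. The error comes from the fork after each high-dose success.
- **The 0.05 is written only in the primary-endpoint paragraph.** A 0.05 level across all six tests is an inference. It is a sound one, because the secondary rule refers back to the primary procedure and says that it covers endpoint order and treatment comparisons together.
- **The decisive phrase is terse, and the SAP, not shown here, may spell it out.** That is possible. But Section 16.2.2.3 defers only the biomarkers to the SAP and writes the secondary rule out itself. Versions 1.0 to 3.0 use the same construction for three regimens, which supports the reading. If one failure ended all testing, limiting the block to the failed comparisons would serve no purpose.

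A reader might also infer that the primary result is compromised. It is not: its high-then-low sequence at 0.05 is a valid fixed sequence.

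**Conclusion.** The rule lacks the property that the protocol claims for it. It is not closed, and it does not control the secondary family-wise error at 0.05 in every configuration.

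The error can reach 0.091 to 0.0975 in the worst case, over an assumed endpoint correlation of 1 down to 0. It is about 0.07 to 0.08 when the gatekeeping high-dose test has 90% power and the correlation is 0.3 to 0.7. It is 0.05 when all secondary nulls are true. These figures rest on normal test statistics, equal arms with a shared placebo group, and the per-regimen reading of the carry-forward sentence.

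The harmful configuration is a plausible one in a two-dose trial: the higher dose helps on one scale but not the next, and the lower dose does not help. The fault is confined to the ranked secondary claims.

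**What to change.** Replace the last sentence of the secondary-endpoint paragraph with one pre-specified list of the six tests, in which the first p > 0.05 ends all further testing for both regimens. Two orders are valid:

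- **High then low within each endpoint.** This keeps the present dose order, but a low-dose failure on MMSE blocks high dose on ADAS-Cog 13.
- **All three high-dose tests, then all three low-dose tests.** This protects the high-dose chain, but low dose on MMSE then depends on high dose succeeding on ADCS-ADL-MCI.

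If both regimens are to advance in parallel, use a graphical procedure that splits 0.05 between them and recycles what is released.

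At the least, state that 0.05 is controlled within each regimen only and that the error across regimens can approach 0.10.

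The change is to wording in the protocol, and in the SAP to match. It needs no new data or subjects, but it must be made before unblinding. The real cost is some secondary power, and the chosen order decides where it is lost.
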